- The monitoring and management of CK values for asymptomatic patients was modified to be consistent with other protocols across the program.
- The Schedule of Events was updated to reflect changes or correct errors.
- Typographical errors and formatting were corrected or revised based on these changes or to improve clarity and consistency.

CHANGE 1 REVISION OF TITLE PAGE VERSION INFORMATION

Location:

Title Page

Original Text:

| | Version | Date | |
|--|---|--------------------|--|
| | Original Protocol: | 01 November 2016 | |
| New Text: | | | |
| | Version | Date | |
| | Original Protocol: | 01 November 2017 | |
| | Amendment 1: | 09 May 2017 | |
| CHANGE 2 Location: | REVISION TO THE DESI | GN SCHEMATIC | |
| Location: | REVISION TO THE DESI is; Section 6.1, Overall Study | | |
| Location: Section 2, Synopsi | | | |

New Text:

CHANGE 3 REVISION OF INCLUSION CRITERIA

Location:

Section 2, Synopsis: Key inclusion criteria; Section 6.7, Patient Inclusion Criteria

Original Text:

1. Successfully completed study ETC-1002-040 (at least 80% investigational medicinal product [IMP]-compliant and able to tolerate IMP at the end of parent study)

- 1. Successfully completed *the parent study (1002-040) and meet both of the following criteria:*ETC-1002-040 (at least 80% investigational medicinal product [IMP]-compliant and able to tolerate IMP at the end of parent study)
 - The patient was compliant with the parent study requirements including study visits, procedures, and investigational medicinal product (IMP) in the opinion of the principal investigator.
 - The patient was able to tolerate IMP through the end of the parent study.

CHANGE 4 REVISION OF EXCLUSION CRITERIA

Location:

Section 2, Synopsis: Key exclusion criteria; Section 6.8, Patient Exclusion Criteria

Original Text:

- 1. Female patient is not willing to use at least 1 highly effective method of birth control during treatment and for an additional 30 days after the end of treatment unless patient is sterilized or postmenopausal;
 - Menopause is defined as greater than 55 years and ≥1 year without menses, less than 55 years and ≥1 year without menses with follicle-stimulating hormone (FSH) ≥40.0 IU/L, or surgically sterile (including hysterectomy and/or bilateral oophorectomy);
 - Acceptable methods of birth control include: oral birth control medications; placement of an intrauterine device (IUD) with or without hormones; barrier methods including condom or occlusive cap with spermicidal foam or spermicidal jelly; vasectomized male partner who is the sole partner for this patient; or true abstinence (not including periodic abstinence such as calendar, ovulation, symptothermal, postovulation methods, or withdrawal).

New Text:

- 1. Female patient is not willing to use at least 1 highly effective acceptable method of birth control during treatment and for an additional 30 days after the end of treatment unless patient is sterilized or postmenopausal;
 - Menopause is defined as greater than 55 years and ≥1 year without menses, less than 55 years and ≥1 year without menses with follicle-stimulating hormone (FSH) ≥40.0 IU/L, or surgically sterile (including hysterectomy and/or bilateral oophorectomy);
 - Acceptable methods of birth control include: oral birth control medications; placement of an intrauterine device (IUD) with or without hormones; barrier methods including condom or occlusive cap with spermicidal foam or spermicidal jelly; vasectomized male partner who is the sole partner for this patient; or true abstinence

where it is the preferred and usual lifestyle of the patient (not including periodic abstinence such as calendar, ovulation, symptothermal, postovulation methods, or withdrawal).

Original Text:

5. Renally impaired patients receiving an average daily dose of simvastatin 40 mg with estimated glomerular filtration rate (eGFR) below <45 mL/min/1.73 m².

New Text:

5. Renally impaired patients receiving an average daily dose of simvastatin 40 mg with estimated glomerular filtration rate (eGFR) below <45 mL/min/1.73 m².

CHANGE 5 REVISION TO PROHIBITED MEDICATIONS

Location:

Section 7.2.1, Prohibited Medications and Supplements

Original Text:

All medications deemed medically necessary may be prescribed during this study, with the following exceptions:

- Mipomersen
- Lomitapide or apheresis therapy
- Red yeast rice containing products
- Uptitration of simvastatin to an average daily dose that is greater than 40 mg
- Gemfibrozil

New Text:

All medications deemed medically necessary may be prescribed during this study, with the following exceptions:

- Mipomersen
- Lomitapide or apheresis therapy
- Red yeast rice containing products
- Uptitration of simvastatin to an average daily*a* dose that is greater than *or equal to* 40 mg/*day*
- Gemfibrozil
- Ezetimibe/simvastatin (Zocor[®]) where simvastatin doses are $\geq 40 \text{ mg/day}$ (Vytorin[®] 10/40 and 10/80 and Inegy[®] 10 mg/40 mg and 10 mg/80 mg are prohibited)

CHANGE 6 REVISION TO BLINDING INSTRUCTIONS

Location:

Section 7.3, Blinding

Original Text:

Laboratory results for lipid panel and hs-CRP will be masked to investigators, patients, and the study team until the Week 12 visit is completed. All site staff involved with this trial should refrain from obtaining lipid panels between date of last ETC-1002-040 dose at end of parent study Week 52 (Visit T7) and Week 12 in this OLE trial.

New Text:

Laboratory results for lipid panel and hs-CRP will be masked to investigators, patients, and the study team until the Week 12 visit is completed. All site staff involved with this trial should refrain from obtaining lipid panels between date of last ETC-1002-040 dose at end of parent study Week 52 (Visit T7) and Week 12 in this OLE trial.

While this is an open-label study where all patients will receive active treatment with bempedoic acid (180 mg by mouth [PO] once daily [QD]), blinding of the treatment that patients received during the parent study must be maintained for all patients unless, in the opinion of the Investigator, the safety of the patient may be at risk. Only under the rarest of circumstances should the Investigator consider breaking the parent study blind and only when medical/supportive care cannot be provided without determining if the patient was previously receiving active drug treatment. In the event that the parent study blind needs to be broken prior to completion of the parent study, the Investigator should contact the appropriate Medical Monitor by telephone. If the parent study blind must be broken prior to consultation with the Medical Monitor, contact must be made within 24 hours of breaking the blind. At the initiation of the study, the clinical site will be instructed on procedures for breaking the blind via the interactive web response system (IWRS) utilized in the parent study. In all cases of breaking the parent study blind, the Investigator must document in the patient's medical record the date, time, and reason for breaking the blind, and the names of personnel involved.

CHANGE 7 REVISION TO PROCEDURES AT ENROLLMENT, EOS/DAY 1 OLE

Location:

Section 9.2.1, Enrollment (EOS/Day 1 OLE)

Original Text:

Day 1 for this study should occur on the same day as the end of study visit for the parent study (1002-040). All efforts should be made to avoid delays in rolling over. The study procedures below, from the parent study EOS visit, will be used to qualify for this study. If Day 1 of the OLE study occurs >30 days from the end of study visit from the parent study, all procedures will need to be repeated including taking a new medical history.

• Review of inclusion/exclusion criteria

- Concomitant medication review
- Assess AE/SAEs
- Physical exam
- Weight (kg)
- Vital signs
- Clinical laboratory evaluations:
 - Hematology, blood chemistry, coagulation (only in patients receiving anticoagulant therapy), and urinalysis
 - Basic fasting lipids (TC, calculated LDL-C, HDL-C, non-HDL-C, and TG)
 - АроВ
 - Hs-CRP
 - Glycosylated hemoglobin, Type A_{1C} (HbA_{1C})
- Urine pregnancy test
- Contact IWRS to register the patient
- Dispense study drug

Day 1 for this study should occur on the same day as the end of study visit for the parent study (1002-040). All efforts should be made to avoid delays in rolling over. The study procedures below, from the parent study EOS visit, will be used to qualify for this study. If Day 1 of the OLE study occurs >30 days from the end of study visit from the parent study, all procedures will need to be repeated including taking a new medical history.

- Review of inclusion/exclusion criteria
- Concomitant medication review
- Assess AE/SAEs
- Physical exam
- Weight (kg)
- Vital signs
- Clinical laboratory evaluations:
 - Hematology, blood chemistry, coagulation (only in patients receiving anticoagulant therapy), and urinalysis
 - Basic fasting lipids (TC, calculated LDL-C, HDL-C, non-HDL-C, and TG)
 - АроВ

- Hs-CRP
- Glycosylated hemoglobin, Type A_{1C} (HbA_{1C})
- Urine pregnancy test
- Contact IWRS to register the patient
- Dispense study drug

Please note the following for patients enrolling into Study 1002-050 within 30 days of completing the EOS visit in the parent study:

- If the patient is not receiving anticoagulant therapy and/or is a woman who is not of childbearing potential, clinical laboratory samples do not need to be collected as the results from the parent study EOS visit will be used for this visit.
- If the patient is receiving anticoagulant therapy, then a coagulation laboratory sample is required at this visit using a Study 1002-050 unscheduled laboratory kit.
- If the patient is a woman of childbearing potential, then a urine pregnancy test is required at this visit.

Please note the following for patients enrolling into Study 1002-050 greater than 30 days after completing the EOS visit in the parent study:

- Clinical laboratory samples should be collected using a Study 1002-050 Day 1 kit. Supplies for collecting the coagulation sample are included in this kit.
- If the patient is a woman of childbearing potential, then a urine pregnancy test is required at this visit.

CHANGE 8 REVISION TO MONITORING AND MANAGEMENT OF ELEVATED CREATINE KINASE

Location:

Section 10.1.4.3.3, Monitoring and Management of Elevated Creatine Kinase

Original Text:

If at any time after enrollment a patient experiences a marked CK elevation $>5 \times$ ULN, the patient will undergo repeat confirmatory assessment as soon as is reasonably possible, preferably within 3 to 7 days of the laboratory result becoming available.

Repeat CK assessment will include query for related symptoms.

• If the repeat CK assessment confirms an unexplained (ie, not associated with recent trauma or physically strenuous activity) CK abnormality >5 × ULN, if asymptomatic the investigator with input from the Sponsor may consider continuing study medication with continued CK assessments every 1-2 weeks.

If at any time after enrollment a patient experiences a marked CK elevation $>5 \times$ ULN, the patient will undergo repeat confirmatory assessment as soon as is reasonably possible, preferably within 3 to 7 days of the laboratory result becoming available.

Repeat CK assessment will include query for related symptoms.

If the repeat CK assessment confirms an unexplained (ie, not associated with recent trauma or physically strenuous activity) CK abnormality >5 × ULN, if asymptomatic the *patient should receive further assessment and investigation into the cause, assess whether there is renal injury, and measure CK approximately weekly or more frequently if clinically indicated until resolution. If CK levels continue to rise, IMP should be discontinued* investigator with input from the Sponsor may consider continuing study medication with continued CK assessments every 1-2 weeks.

CHANGE 9 REVISION TO LIPID MEASUREMENTS

Location:

Section 10.1.4.4.1, Lipid Measurements

Original Text:

Investigators, site staff, patients, and the study team will be masked to study lipid levels as well as ApoB and hs-CRP until the Week 12 study visit, after which time lipid values will be made available and concomitant medications may be adjusted as necessary.

• The initiation of any new or dose changes of any existing lipid-lowering treatment will be documented on the eCRF as a concomitant medication with the associated start date. Uptitration of simvastatin to an average daily dose that is greater than 40 mg is not permitted.

New Text:

Investigators, site staff, patients, and the study team will be masked to study lipid levels as well as ApoB and hs-CRP until the Week 12 study visit, after which time lipid values will be made available and concomitant medications may be adjusted as necessary.

• The initiation of any new or dose changes of any existing lipid-lowering treatment will be documented on the eCRF as a concomitant medication with the associated start date. Uptitration of simvastatin to an average daily dose that is greater than *or equal to* 40 mg is not permitted.

CHANGE 10 REVISION TO APPENDIX 1

Location:

Appendix 1: Schedule of Events (Patient Visit Schedule)

Original Text:

| Month | 0 | 3 | 6 | 9 | 12 | 15 | 18/EOS ¹ |
|-----------------------------------|-------------------|---------|---------|---------|---------|---------|---------------------|
| Week | EOS Parent | Wk 12 | Wk 24 | Wk 36 | Wk 52 | Wk 64 | Wk 78 |
| Visit Window | 30 Days pre-M0 | ±7 days |
| In-clinic Visit | X | X | | | X | | X |
| Phone Visit | | | X | X | | X | |
| Procedure | | | | | | | |
| Informed Consent | Х | | | | | | |
| Enrollment Criteria | Х | | | | | | |
| Medical History | Х | | | | | | |
| Concomitant Medications | Х | Х | X | X | X | X | Х |
| Adverse Event Recording | Х | Х | Х | X | X | X | Х |
| Physical Exam | Х | | | | Х | | Х |
| Weight ² | Х | Х | | | Х | | Х |
| Vital Signs ³ | Х | Х | | | X | | Х |
| Urine Pregnancy Test | Х | | | | | | |
| Clinical Safety Labs ⁴ | Х | Х | | | X | | Х |
| Basic Fasting Lipids ⁵ | Х | Х | | | Х | | Х |
| Coagulation ⁶ | Х | | | | | | |
| ApoB and hsCRP | Х | Х | | | X | | Х |
| HbA _{1C} | Х | | | | Х | | Х |
| IWRS Contact ⁷ | Х | Х | | | Х | | Х |
| Drug Dispensing | Х | Х | | | Х | | |
| Drug Return/Compliance | | Х | | | Х | | Х |

NOTE: For patients who withdraw from study drug treatment, but consent to be followed for safety assessments and return to clinic for these visit, the visits will occur according to the protocol schedule. Safety assessments should include clinical safety and basic lipid laboratories, adverse events (AEs), physical examination (PE), vital signs, and electrocardiograms (ECGs). For patients who withdraw from study drug treatment, but consent to be followed for safety assessments by phone, the telephone contacts will occur according the protocol schedule with information regarding current health status and to collect information on AEs (eg, recent procedures, hospitalizations, and if the

patient has died, the cause of death). If a patient does not provide consent to be followed for safety assessments per the protocol (either by returning to clinic or by phone), Visit week 78 will be considered the End of Study (EOS)/Early Withdrawal from study and no further visits will be scheduled.

- ¹ All procedures will be completed for all patients at either EOS if completing the study or early withdrawal.
- ² Body weight will be measured in the morning while fasting, using consistent scales, after voiding, and without shoes and outerwear (eg, coats).
- ³ Vital signs will include diastolic blood pressure (DBP), systolic blood pressure (SBP), heart rate (HR) and will be collected prior to any blood sample collection. Patient will rest for 5 minutes prior to assessments
- ⁴ Clinical safety labs include hematology, blood chemistry, and urinalysis at all visits. Please refer to laboratory manual for detailed schedule of tests.
- ⁵ Basic fasting lipids include total cholesterol (TC), calculated low-density lipoprotein cholesterol (LDL-C), highdensity lipoprotein cholesterol (HDL-C), non-HDL-C,), and triglycerides (TG).
- ⁶ Only in patients receiving anticoagulant therapy that in the investigator's judgment require monitoring at Month 0 and 3 to 5 days post-Month 0
- ⁷ Interactive web response system (IWRS) contact at either an early withdrawal or an EOS visit to register study discontinuation visit date

| Month | 0 | 3 | 6 | 9 | 12 | 15 | 18/EOS ¹ |
|------------------------------------|-------------------|---------|---------|---------|---------|---------|---------------------|
| Week | EOS Parent | Wk 12 | Wk 24 | Wk 36 | Wk 52 | Wk 64 | Wk 78 |
| Visit Window | 30 Days pre-M0 | ±7 days |
| In-clinic Visit | X | X | | | X | | X |
| Phone Visit | | | X | X | | X | |
| Procedure | | | | | | | |
| Informed Consent | Х | | | | | | |
| Enrollment Criteria | Х | | | | | | |
| Medical History | Х | | | | | | |
| Concomitant Medications | Х | Х | Х | Х | X | Х | Х |
| Adverse Event Recording | Х | Х | Х | Х | X | Х | Х |
| Physical Exam | Х | | | | Х | | Х |
| Weight ² | Х | Х | | | Х | | Х |
| Vital Signs ³ | Х | Х | | | Х | | Х |
| Urine Pregnancy Test ⁴ | Х | | | | | | |
| Clinical Safety Labs ⁴⁵ | Х | Х | | | Х | | Х |
| Basic Fasting Lipids ⁵⁶ | Х | Х | | | Х | | Х |
| Coagulation ⁶⁷ | Х | | | | | | |
| ApoB and hsCRP | Х | Х | | | Х | | Х |
| HbA _{1C} | Х | | | | Х | | Х |

New Text:

| IWRS Contact ⁷⁸ | Х | Х | | Х | Х |
|----------------------------|---|---|--|---|---|
| Drug Dispensing | Х | Х | | Х | |
| Drug Return/ Compliance | | Х | | Х | Х |

NOTE: For patients who withdraw from study drug treatment, but consent to be followed for safety assessments and return to clinic for these visit, the visits will occur according to the protocol schedule. Safety assessments should include clinical safety and basic lipid laboratories, adverse events (AEs), physical examination (PE), *and* vital signs, and electrocardiograms (ECGs). For patients who withdraw from study drug treatment, but consent to be followed for safety assessments by phone, the telephone contacts will occur according the protocol schedule with information regarding current health status and to collect information on AEs (eg, recent procedures, hospitalizations, and if the patient has died, the cause of death). If a patient does not provide consent to be followed for safety assessments per the protocol (either by returning to clinic or by phone), Visit week 78 will be considered the End of Study (EOS)/Early Withdrawal from study and no further visits will be scheduled.

¹ All procedures will be completed for all patients at either EOS if completing the study or early withdrawal.

- ² Body weight will be measured in the morning while fasting, using consistent scales, after voiding, and without shoes and outerwear (eg, coats).
- ³ Vital signs will include diastolic blood pressure (DBP), systolic blood pressure (SBP), heart rate (HR) and will be collected prior to any blood sample collection. Patient will rest for 5 minutes prior to assessments

⁴ Urine pregnancy test in women of childbearing potential only

⁴⁵Clinical safety labs include hematology, blood chemistry, and urinalysis at all visits. Please refer to laboratory manual for detailed schedule of tests.

⁵⁶Basic fasting lipids include total cholesterol (TC), calculated low-density lipoprotein cholesterol (LDL-C), highdensity lipoprotein cholesterol (HDL-C), non-HDL-C,), and triglycerides (TG).

⁶⁷Only in patients receiving anticoagulant therapy that in the investigator's judgment require monitoring at Month 0 and 3 to 5 days post-Month 0

CHANGE 11 REMOVED FINAL DATE

Location:

Appendix 2: Final Date, all pages within Appendix 2 and Appendix 3

Original text:

Final Date:01 November 2016

New text:

Final Date: 01 November 2016

⁷⁸Interactive web response system (IWRS) contact at either an early withdrawal or an EOS visit to register study discontinuation visit date

CHANGE 12 CHANGE IN SPONSOR REPRESENTATIVES PROVIDING PROTOCOL SIGNAGE

Location:

- Revised the study design to include an assessment at Week 82, 4 weeks after patients have completed their last dose of bempedoic acid. This assessment was added to have safety and efficacy data off study drug to help interpret any potential findings during the treatment period.
- Updated the design schematic to include the 4-week follow-up period from Week 78 to Week 82.
- Week 78 is now called the End of Treatment (EOT) visit and Week 82 is described as the Off Study Drug Period/End of Study (EOS) visit.
- The section on Background of Bempedoic Acid has been updated to reflect the current version of the Investigator's Brochure.

- The section on Concomitant Medications has been revised to avoid changes in lipidlowering medications during the 4-week washout period to limit the introduction of medications that may affect endpoints of interest measured at Week 82.
- The statistical analysis plan for renal events was updated to remove text that indicated muscle related events would be analyzed based on baseline eGFR. There is no data or clinical justification to justify assessment of muscle related events by eGFR.
- Text throughout the protocol was updated to reflect the addition of the 4-week follow-up period.
- Typographical errors and formatting were corrected or revised based on these changes or to improve clarity and consistency.

| Location: | |
|------------------------|-----|
| Title Page | |
| Original Text: | |
| Sponsor Contact | |
| Medical Monitor | •• |
| New Text: | |
| Sponsor Contact | • • |
| Medical Monitor | •• |

CHANGE 1 REVISION OF TITLE PAGE VERSION INFORMATION

Original Text:

| | Version | Date | |
|-----------|--------------------|------------------|--|
| | Original Protocol: | 01 November 2017 | |
| | Amendment 1: | 9 May 2017 | |
| New Text: | | | |
| | Version | Date | |
| | Original Protocol: | 01 November 2017 | |
| | | | |
| | Amendment 1: | 09 May 2017 | |

CHANGE 2 REVISION TO THE STUDY DESIGN TO INCLUDE A 4 WEEK FOLLOW UP PERIOD AFTER WEEK 78

Location:

Section 2, Synopsis; Section 6.1, Overall Study Design; Section 6.3, Study Duration; Section 6.4, End of Study; Section 9.2.6, Treatment Month 18; Section 9.2.7, Washout Month 19; Section 9.3.1, Early Withdrawal from the Study; Section 9.3.2, Procedures for Early Withdrawal

Original Text:

This is a multicenter OLE study designed to assess the long-term safety and efficacy of bempedoic acid (ETC-1002) 180 mg. All patients will receive open-label bempedoic acid 180 mg for up to 1.5 years after rolling over from the parent study (Study 1002-040). Investigators, site staff, patients, and the study team will be masked to study lipid levels until the Week 12 study visit, after which time lipid values will be made available.

New Text:

Extension Design Options

This is a multicenter OLE study designed to assess the long-term safety and efficacy of bempedoic acid (ETC-1002) 180 mg. All patients will receive open-label bempedoic acid 180 mg for up to 1.5 years after rolling over from the parent study (Study 1002-040) *followed by a follow-up period off study drug for 4 weeks*. Investigators, site staff, patients, and the study team will be masked to study lipid levels until the Week 12 study visit, after which time lipid values will be made available.

Original Text:

Duration of treatment:

The total duration of treatment for an individual subject will be 1.5 years.

Duration of treatment:

The total duration of treatment for an individual subject will be 1.5 years (18 months). The total duration in the study will be 19 months.

Original Text:

This is a multicenter open-label extension (OLE) study designed to assess the long-term safety and efficacy of bempedoic acid 180 mg. All patients will receive open-label bempedoic acid 180 mg for up to 1.5 years after rolling over from Study 1002-040 (parent study). Investigators, site staff, patients, and the study team will be masked to study lipid levels until the Week 12 study visit, after which time lipid values will be made available to sites. The study will be conducted at approximately 125 clinical sites in the US, Canada, Germany, Netherlands, Poland, and United Kingdom. It's anticipated that approximately 1300 patients will elect to enroll into this study. Patients will have visits every 3 months. Patients will be required to visit the site at baseline (end of study [EOS] parent), Week 12, Week 52, and Week 78. Phone visits will occur at Weeks 24, 36, and 64.

New Text:

This is a multicenter open-label extension (OLE) study designed to assess the long-term safety and efficacy of bempedoic acid 180 mg. All patients will receive open-label bempedoic acid 180 mg for up to 1.5 years after rolling over from Study 1002-040 (parent study) *followed by a period off study drug for 4 weeks*. Investigators, site staff, patients, and the study team will be masked to study lipid levels until the Week 12 study visit, after which time lipid values will be made available to sites. The study will be conducted at approximately 125 clinical sites in the US, Canada, Germany, Netherlands, Poland, and United Kingdom. It's anticipated that approximately 1300 patients will elect to enroll into this study. Patients will have visits every 3 months. Patients will be required to visit the site at baseline (end of study [EOS] parent), Week 12, Week 52, *Week 78*, and Week 7882. Phone visits will occur at Weeks 24, 36, and 64.

Original Text:

Patients will be enrolled after successfully completing study ETC-1002-040. The total study duration for an individual subject is 1.5 years.

New Text:

Patients will be enrolled after successfully completing study ETC-1002-040. The total study duration for an individual subject is 1.5 years 82 weeks (1 year and 7 months).

Original Text:

The study will end when the last patient completes their Week 78 visit. The estimated overall duration of the study (first patient first visit [FPFV] to last patient last visit [LPLV]) is approximately 2.5 years.

New Text:

The study will end when the last patient completes their Week **7882** visit. The estimated overall duration of the study (first patient first visit [FPFV] to last patient last visit [LPLV]) is approximately 2.5 years.

Original Text:

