7.2. Concomitant Medications

During the study investigators may prescribe any necessary concomitant medication. However, lipid-altering therapies cannot be adjusted during the first 12 weeks of the study. In addition, during the 4-week period after last dose, every effort should be made to maintain the patients' background lipid-modifying therapy unless it is medically necessary to safely manage the patient. Patients will be questioned about their concomitant medication use at each clinic visit. All concomitant medication taken chronically or intermittently during the study must be recorded with indication, total daily dose, and start and stop dates of administration. Prior and concomitant medications will be collected using an electronic case report form (eCRF).

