9.2.7. Off Study Drug Period Month 19/EOS (Week 82 +14 days)

Patients will return for a final EOS visit 4 weeks after IMP treatment has been completed (including patients who withdraw from IMP treatment prior to Week 78) to undergo the following assessments and procedures.

- Concomitant medication review
- Assess AEs, SAEs, and potential clinical endpoints
- Weight
- Vital signs
- Clinical laboratory evaluations:
 - hematology, blood chemistry, and urinalysis
 - Basic fasting lipids (TC, calculated LDL C, HDL C, non-HDL C, and TG)
 - ApoB and hs-CRP
 - HbA_{1C}

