- ¹ All procedures will be completed for all patients at either EOT or early withdrawal.
- ² All procedures will be completed for all patients 4 weeks after last IMP dose if completing the study or early withdrawal.
- ³ Body weight will be measured in the morning while fasting, using consistent scales, after voiding, and without shoes and outerwear (eg, coats).
- ⁴ Vital signs will include diastolic blood pressure (DBP), systolic blood pressure (SBP), heart rate (HR) and will be collected prior to any blood sample collection. Patient will rest for 5 minutes prior to assessments
- ⁵ Urine pregnancy test in women of childbearing potential only
- ⁶ Clinical safety labs include hematology, blood chemistry, and urinalysis at all visits. Please refer to laboratory manual for detailed schedule of tests.
- ⁷ Basic fasting lipids include total cholesterol (TC), calculated low-density lipoprotein cholesterol (LDL-C), highdensity lipoprotein cholesterol (HDL-C), non-HDL-C,), and triglycerides (TG).
- ⁸ Only in patients receiving anticoagulant therapy that in the investigator's judgment require monitoring at Month 0 and 3 to 5 days post-Month 0
- ⁹ Interactive web response system (IWRS) contact at either an early withdrawal or an EOS visit to register study discontinuation visit date

Bempedoic Acid Clinical Study Protocol 1002-050

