#### 5.2.7 Concomitant Medications

Concomitant medications are defined as medications that were ongoing at the time of study drug initiation in this OLE study or new medications that started post study drug initiation and within 30 days following the date of the last dose of study drug.

Medications, including lipid modifying therapy (LMT) medications, will be coded using WHO Drug (March, 2017, or later if appropriate). The frequency of use of concomitant medications will be summarized by previous treatment group in parent study, as well as overall in OLE study, for the safety population according to Anatomical Therapeutic Chemical (ATC) class and preferred term. Concomitant medications will be listed for each patient. Concomitant LMT medications will be summarized by ATC class and medication name and listed separately in a similar fashion.

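### Background lipid therapy is to be kept stable for 4 weeks after the last dose, but the Week 82 lipid sample may come 2 weeks later, and the SAP stops counting new drugs at 30 days

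*Protocol*

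**What the plan says.** The operative text is Protocol Section 7.2: "during the 4-week period after last dose, every effort should be made to maintain the patients' background lipid-modifying therapy unless it is medically necessary" for managing the patient safely. Appendix 5, which summarises Amendment 2, gives the purpose of that request: "to limit the introduction of medications that may affect endpoints of interest measured at Week 82". Outside that period and the first 12 weeks, Section 7.2 lets investigators prescribe what they judge necessary. Section 10.1.4.4.1 confirms that lipid therapy may be adjusted after Week 12, subject to the prohibited list in Section 7.2.1. No passage carries the request forward to the day on which the Week 82 blood is actually drawn.

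The visit is headed "Off Study Drug Period Month 19/EOS (Week 82 +14 days" and described thus: "Patients will return for a final EOS visit 4 weeks after IMP treatment has been completed". A footnote to Appendix 1 ties it to the last dose: "All procedures will be completed for all patients 4 weeks after last IMP dose if completing the study or early withdrawal". Fasting lipids, ApoB and hs-CRP are drawn at that visit.

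SAP version 1.3 adds a third limit. Section 5.2.7 defines a new drug as concomitant only if it started "within 30 days following the date of the last dose of study drug", and the summary and listing of lipid-modifying therapy rest on that definition. Section 5.3 includes Week 82 among the visits summarised, uses all observed values, and has no rule for a value drawn after a change in lipid therapy. The analysis window for Week 82 in Section 5.1 opens at Day 563 and has no upper limit.

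**The concern.** Three periods that all bear on the Week 82 lipid values end on different days: the request to keep therapy stable, the counting of new drugs, and the permitted time of the sample. A site can follow the protocol exactly, start lipid therapy after the fourth week, draw the sample in the sixth, and commit no deviation. The resulting value then enters the summary as an off-drug value, and the lipid-therapy table need not show that anything was started.

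Amendment 2 added the visit to obtain safety and efficacy data off study drug that help interpret findings during treatment, and it added the Section 7.2 request to protect those data. New or increased lipid-lowering therapy before the sample would lower LDL-C. To a reader comparing Week 82 with Week 78, the return after stopping would then look smaller than it was.

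**Working it through.** No error rate or sample size is involved, so the check is calendar arithmetic.

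**The plan's own figures.** SAP Section 5.1 gives target days 546 and 574. These reproduce: 78 × 7 = 546, 82 × 7 = 574, and 574 − 546 = 28 days, the nominal 4 weeks off drug.

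**Counted from last dose, as Section 9.2.7 and the Appendix 1 footnote do.**

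| Period | Source | Last day |
|---|---|---|
| Request to keep lipid therapy stable | Protocol 7.2 | 28 |
| New drugs counted as concomitant | SAP 5.2.7 | 30 |
| Latest in-window Week 82 sample | Protocol 9.2.7, Appendix 1 | 28 + 14 = 42 |

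- Days on which the sample is permitted but the request has lapsed: 42 − 28 = 14 (Days 29 to 42).
- Days on which a new drug also escapes the concomitant definition: 42 − 30 = 12 (Days 31 to 42).
- Longest exposure to a drug started once the request has lapsed: Day 29 to Day 42, 42 − 29 = 13 days.
- Longest exposure to a drug missing from the table: Day 31 to Day 42, 42 − 31 = 11 days.

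**Counted from study Day 1.** If the 14 days run from Day 574, the latest sample is Day 588. With Week 78 at 546 ± 7, the last dose falls on Days 539 to 553, so the latest sample is 588 − 553 = 35 to 588 − 539 = 49 days after last dose. The uncovered stretch is then 7 to 21 days, and the longest exposure to a drug started on Day 29 is 49 − 29 = 20 days. The gap exists on either count; only its length changes.

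**What the table can show.** The summary is by drug class and name over the whole study. A start on Days 29 or 30 is counted but not linked to the Week 82 value. A dose increase of a drug already in use adds nothing to the table at any time. Dates of starts and dose changes are nevertheless collected: Sections 7.2 and 10.1.4.4.1 require them on the eCRF, and medication is reviewed at Week 82.

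**A related discrepancy.** SAP Section 5.1 gives the protocol window for Week 82 as 574 ± 14. The protocol allows only the 14 days after.

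**The case against.** The case that this matters little is strong, and most of it stands.

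- Section 7.2 is a request with a medical exception, and its stated aim is to limit new medication, not exclude it. Some change of therapy is accepted even within the 4 weeks, and a late tolerance on a nominal 4-week visit does not formally contradict such a request.
- The visit is aimed at exactly 4 weeks. A patient seen then is covered, and only those seen later are exposed.
- Appendix 1 schedules no visit, call or lipid sample between Week 78 and Week 82, so the latest scheduled lipid result a site holds is an on-drug one. Section 4.2.5 describes patients already on maximally tolerated lipid-modifying therapy.
- The named secondary endpoints are at Weeks 52 and 78. The study is descriptive, and no change from Week 78 to Week 82 is planned.
- The safety purpose of the visit is untouched, and no data are lost: the gap is in a table definition.
- Leaving out values drawn after a therapy change conditions on something that happens after withdrawal. It may remove those judged to need more treatment, which could itself make the return look smaller.

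These points limit the size and shape the remedy. They do not close the gap: the periods still end on different days, and the SAP would include an affected value without showing why.

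A reader might go further and infer that most Week 82 samples are contaminated, since 14 of the 15 permitted days (28 to 42) fall after the request lapses. That counts days, not patients, and the documents do not say how many are seen late. A reader might also infer that replacement therapy is especially likely at this point. Nothing in the schedule supports that.

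**Conclusion.** The mismatch is real and lies in the current text of Protocol Sections 7.2 and 9.2.7, Appendix 1, and SAP Sections 5.2.7 and 5.3. In patients sampled after Day 28, lipid therapy may have been started or raised within the rules; if it was started after Day 30, the lipid-therapy summary omits it. The likely direction is towards lower off-drug LDL-C.

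The size is unknown. The documents give neither the share sampled late nor the share who change therapy, so no figure in percentage points can be supported. It is probably small, because on the count from last dose any such therapy is under about two weeks old (up to 20 days on the least favourable count from Day 1). The effect is confined to the descriptive Week 82 lipid summary; the Week 52 and Week 78 endpoints are not touched. A reader might conclude that the visit fails in its purpose. The documents do not support that: its safety use is intact, and patients seen on time are covered.

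This is a cheap improvement, not a flaw that threatens a planned conclusion.

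**What to change.** 1. **Protocol.** Reconcile the period in Section 7.2 with the Week 82 window in Section 9.2.7 and Appendix 1. How to do so is the sponsor's decision. Correct the Week 82 window shown in SAP Section 5.1 at the same time.
2. **SAP Section 5.2.7.** For lipid-modifying therapy, count use to the later of 30 days after last dose and the date of the Week 82 sample.
3. **SAP Section 5.3.** Keep the Week 82 summary of all observed values. Add a sensitivity summary without values drawn after a lipid-therapy start or dose change since last dose. Label it as such, and state that it has a smaller n and conditions on an event after withdrawal, so it is to be read beside the main summary and not in its place.

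The cost is one wording alignment in the protocol, a sentence or two in each of two SAP sections, a corrected window entry, and one extra table. No new data are needed. If the protocol can no longer be changed, the SAP changes still work alone.
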